	Effective Date:	25-Nov-2021

Listing 16.2.4. Listing of Overall Investigators Assessment

Patient No	Visit	Overall Investigators Assessment performed	If Yes
xx-XXX	xxxx	Yes/No	Well controlled/Partly controlled/Uncontrolled
xx-XXX	xxxx	Yes/No	Well controlled/Partly controlled/Uncontrolled
xx-XXX	xxxx	Yes/No	Well controlled/Partly controlled/Uncontrolled
xx-XXX	xxxx	Yes/No	Well controlled/Partly controlled/Uncontrolled
xx-XXX	xxxx	Yes/No	Well controlled/Partly controlled/Uncontrolled

Document Title:	Document ID:	BP04-01
Statistical Analysis Plan	Version Number:	3.1
	Effective Date:	25-Nov-2021

[Listing 16.3.1.1. Listing of Patient Adverse Event Assessment](#)

Patient No	Visit	Patient Experience any adverse event since ICF obtained	Patient Experience any new adverse event or change in existing adverse event since ICF obtained
xx-xxx	xxxx	Yes/No	Yes/No
xx-xxx	xxxx	Yes/No	Yes/No
xx-xxx	xxxx	Yes/No	Yes/No
xx-xxx	xxxx	Yes/No	Yes/No
xx-xxx	xxxx	Yes/No	Yes/No

Document Title:		Document ID:	BP04-01
Statistical Analysis Plan		Version Number:	3.1
Effective Date:		25-Nov-2021	

Listing 16.3.1.2. Listing of Patient Adverse Events

Patient No	Patient Experience any Adverse Event		Seq. No.	Event Description	Start Date/ Stop Date	Investigators causality rating against the Investigational Product		Action taken	Patient Withdrawn	Treatment taken	Outcome	SAE
	Ongoing	Intensity										
xx-xxx	Yes/No	Xx	Xxxx	DD-MMM-YYYY/ DD-MMM-YYYY	Xxxx	Xxxx	Yes/No	Xxxx	Yes/No	Xxxx	Xxxx	Yes/No
xx-xxx	Yes/No	Xx	Xxxx	DD-MMM-YYYY/ DD-MMM-YYYY	Xxxx	Xxxx	Yes/No	Xxxx	Yes/No	Xxxx	Xxxx	Yes/No
xx-xxx	Yes/No	Xx	Xxxx	DD-MMM-YYYY/ DD-MMM-YYYY	Xxxx	Xxxx	Yes/No	Xxxx	Yes/No	Xxxx	Xxxx	Yes/No
xx-xxx	Yes/No	Xx	Xxxx	DD-MMM-YYYY/ DD-MMM-YYYY	Xxxx	Xxxx	Yes/No	Xxxx	Yes/No	Xxxx	Xxxx	Yes/No
xx-xxx	Yes/No	xx	Xxxx	DD-MMM-YYYY	Xxxx	Xxxx	Yes/No	Xxxx	Yes/No	Xxxx	Xxxx	Yes/No

Document Title:	Document ID:	BP04-01
Statistical Analysis Plan	Version Number:	3.1
	Effective Date:	25-Nov-2021

Listing 16.3.2.1. Listing of Patient Serious Adverse Events (Part 1)

Patient		Date of AE met criteria for SAE	Date of Investigator became aware of Serious AE	Patient		Date of Hospitalized due to SAE	Date of Hospitalized	Date of Discharge	Seriousness Criteria	Date of Event Onset
No	Age	Gender	SAE term	Hospitalized	due to SAE					
xx-xxx	Xx	Xx	Xxxx	DD-MMM-YYYY	DD-MMM-YYYY	Yes/No	DD-MMM-YYYY	DD-MMM-YYYY	Xxxx	DD-MMM-YYYY
xx-xxx	Xx	Xx	Xxxx	DD-MMM-YYYY	DD-MMM-YYYY	Yes/No	DD-MMM-YYYY	DD-MMM-YYYY	Xxxx	DD-MMM-YYYY
xx-xxx	Xx	Xx	Xxxx	DD-MMM-YYYY	DD-MMM-YYYY	Yes/No	DD-MMM-YYYY	DD-MMM-YYYY	Xxxx	DD-MMM-YYYY
xx-xxx	Xx	Xx	Xxxx	DD-MMM-YYYY	DD-MMM-YYYY	Yes/No	DD-MMM-YYYY	DD-MMM-YYYY	Xxxx	DD-MMM-YYYY
xx-xxx	xx	xx	Xxxx	DD-MMM-YYYY	DD-MMM-YYYY	Yes/No	DD-MMM-YYYY	DD-MMM-YYYY	Xxxx	DD-MMM-YYYY

Document Title:	Document ID:	BP04-01
Statistical Analysis Plan	Version Number:	3.1
	Effective Date:	25-Nov-2021

Listing 16.3.2.2. Listing of Patient Serious Adverse Events (Part 2)

Patient No	Causality assessment in relation to study Procedure	Causality assessment in relation to other medication	Outcome	Recovered with sequelae date	Probable Cause of Death	Autopsy Performed	Date of Autopsy
xx-xxx	Yes/No	Yes/No	XXXX	DD-MMM-YYYY	xxxx	Yes/No	DD-MMM-YYYY
xx-xxx	Yes/No	Yes/No	XXXX	DD-MMM-YYYY	DD-MMM-YYYY	Yes/No	DD-MMM-YYYY
xx-xxx	Yes/No	Yes/No	XXXX	DD-MMM-YYYY	DD-MMM-YYYY	Yes/No	DD-MMM-YYYY
xx-xxx	Yes/No	Yes/No	XXXX	DD-MMM-YYYY	DD-MMM-YYYY	Yes/No	DD-MMM-YYYY
xx-xxx	Yes/No	Yes/No	XXXX	DD-MMM-YYYY	DD-MMM-YYYY	Yes/No	DD-MMM-YYYY

Document Title:	Document ID:	BP04-01
Statistical Analysis Plan	Version Number:	3.1
	Effective Date:	25-Nov-2021

Listing 16.3.3.1. Listing of Patient Haematology Parameters

Patient No	Visit	Blood Sample Collected	Date and Time of Blood sample	Parameter	Result	Unit	Reference Range	Clinical Significance	If Abnormal CS/NCS
xx-XXX	xxxx	Yes/No	DD-MMM-YYYY/HH:MM	xxxx	xxxx	xxxx	xxxx	Normal / Abnormal	xxxx
xx-XXX	xxxx	Yes/No	DD-MMM-YYYY/HH:MM	xxxx	xxxx	xxxx	xxxx	Normal / Abnormal	xxxx
xx-XXX	xxxx	Yes/No	DD-MMM-YYYY/HH:MM	xxxx	xxxx	xxxx	xxxx	Normal / Abnormal	xxxx
xx-XXX	xxxx	Yes/No	DD-MMM-YYYY/HH:MM	xxxx	xxxx	xxxx	xxxx	Normal / Abnormal	xxxx
xx-XXX	xxxx	Yes/No	DD-MMM-YYYY/HH:MM	xxxx	xxxx	xxxx	xxxx	Normal / Abnormal	xxxx

Document Title:	Document ID:	BP04-01
Statistical Analysis Plan	Version Number:	3.1
	Effective Date:	25-Nov-2021

Listing 16.3.3.2. Listing of Patient Biochemistry Parameters

Patient No	Visit	Blood Sample Collected	Date and Time of Blood sample	Parameter	Result	Unit	Reference Range	Clinical Significance	If Abnormal CS/NCS
XX-XXX	xxxx	Yes/No	DD-MMM-YYYY/HH:MM	xxxx	xxxx	xxxx	xxxx	Normal / Abnormal	Xxxx
XX-XXX	xxxx	Yes/No	DD-MMM-YYYY/HH:MM	xxxx	xxxx	xxxx	xxxx	Normal / Abnormal	Xxxx
XX-XXX	xxxx	Yes/No	DD-MMM-YYYY/HH:MM	xxxx	xxxx	xxxx	xxxx	Normal / Abnormal	Xxxx
XX-XXX	xxxx	Yes/No	DD-MMM-YYYY/HH:MM	xxxx	xxxx	xxxx	xxxx	Normal / Abnormal	Xxxx
XX-XXX	xxxx	Yes/No	DD-MMM-YYYY/HH:MM	xxxx	xxxx	xxxx	xxxx	Normal / Abnormal	Xxxx

Document Title:	Document ID:	BP04-01
Statistical Analysis Plan	Version Number:	3.1
	Effective Date:	25-Nov-2021

Listing 16.3.3.3. Listing of Patient Urinalysis Parameters

Patient No	Visit	Blood Sample Collected	Date and Time of Urine sample	Parameter	Result	Unit	Reference Range	Clinical Significance	If Abnormal CS/NCS
XX-XXX	xxxx	Yes/No	DD-MMM-YYYY/HH:MM	xxxx	xxxx	xxxx	xxxx	Normal / Abnormal	xxxx
XX-XXX	xxxx	Yes/No	DD-MMM-YYYY/HH:MM	xxxx	xxxx	xxxx	xxxx	Normal / Abnormal	xxxx
XX-XXX	xxxx	Yes/No	DD-MMM-YYYY/HH:MM	xxxx	xxxx	xxxx	xxxx	Normal / Abnormal	xxxx
XX-XXX	xxxx	Yes/No	DD-MMM-YYYY/HH:MM	xxxx	xxxx	xxxx	xxxx	Normal / Abnormal	xxxx
XX-XXX	xxxx	Yes/No	DD-MMM-YYYY/HH:MM	xxxx	xxxx	xxxx	xxxx	Normal / Abnormal	xxxx

Document Title:	Document ID:	BP04-01
Statistical Analysis Plan	Version Number:	3.1
	Effective Date:	25-Nov-2021

Listing 16.3.3.4. Listing of Patient Serum Pregnancy Test

Patient No	Visit	Serum Pregnancy test performed	Date and Time of Assessment	Result
XX-XXX	XX-XXX	Yes/No	DD-MMM-YYYY/HH:MM	Positive/Negative
XX-XXX	XX-XXX	Yes/No	DD-MMM-YYYY/HH:MM	Positive/Negative
XX-XXX	XX-XXX	Yes/No	DD-MMM-YYYY/HH:MM	Positive/Negative
XX-XXX	XX-XXX	Yes/No	DD-MMM-YYYY/HH:MM	Positive/Negative
XX-XXX	XX-XXX	Yes/No	DD-MMM-YYYY/HH:MM	Positive/Negative

Document Title:	Document ID:	BP04-01
Statistical Analysis Plan	Version Number:	3.1
	Effective Date:	25-Nov-2021

Listing 16.3.4. Listing of Patient Vital Signs

Patient No	Visit	Vital signs collected	If No, Specify reason	Parameter	Result	Unit	Assessment	If Abnormal CS/NCS
xx-xxx	xxxx	Yes/No	Xxxx	Xxxx	Xxxx	Xxxx	Normal/Abnormal	Xxxx
xx-xxx	xxxx	Yes/No	Xxxx	Xxxx	Xxxx	Xxxx	Normal/Abnormal	Xxxx
xx-xxx	xxxx	Yes/No	Xxxx	Xxxx	Xxxx	Xxxx	Normal/Abnormal	Xxxx
xx-xxx	xxxx	Yes/No	Xxxx	Xxxx	Xxxx	Xxxx	Normal/Abnormal	Xxxx
xx-xxx	xxxx	Yes/No	xxxx	xxxx	xxxx	xxxx	Normal/Abnormal	xxxx

Document Title:		Document ID:	BP04-01
Statistical Analysis Plan		Version Number:	3.1
		Effective Date:	25-Nov-2021

Listing 16.3.5. Listing of Patient Electrocardiogram (ECG)

Patient No	Visit	ECG Performed	If No, Specify reason	Parameter	Result	Unit	Assessment	If Abnormal CS/NCS
XX-XXX	xxxx	Yes/No	Xxxx	Xxxx	Xxxx	Xxxx	Normal/Abnormal	Xxxx
XX-XXX	xxxx	Yes/No	Xxxx	Xxxx	Xxxx	Xxxx	Normal/Abnormal	Xxxx
XX-XXX	xxxx	Yes/No	Xxxx	Xxxx	Xxxx	Xxxx	Normal/Abnormal	Xxxx
XX-XXX	xxxx	Yes/No	Xxxx	Xxxx	Xxxx	Xxxx	Normal/Abnormal	Xxxx
XX-XXX	xxxx	Yes/No	xxxx	xxxx	xxxx	Xxxx	Normal/Abnormal	xxxx

Document Title:		Document ID:	BP04-01
Statistical Analysis Plan		Version Number:	3.1
		Effective Date:	25-Nov-2021

Listing 16.3.6. Listing of Patient Targeted Physical Examination

Patient No	Visit	Physical Examination performed	If No, Specify reason	Date of Physical Examination	Seq. No	System	Assessment	If Abnormal CS/NCS
XX-XXX	xxxx	Yes/No	Xxxx	DD-MMM-YYYY	Xxxx	Xxxx	Normal/Abnormal	Xxxx
XX-XXX	xxxx	Yes/No	Xxxx	DD-MMM-YYYY	Xxxx	Xxxx	Normal/Abnormal	Xxxx
XX-XXX	xxxx	Yes/No	Xxxx	DD-MMM-YYYY	Xxxx	Xxxx	Normal/Abnormal	Xxxx
XX-XXX	xxxx	Yes/No	Xxxx	DD-MMM-YYYY	Xxxx	Xxxx	Normal/Abnormal	Xxxx
XX-XXX	xxxx	Yes/No	xxxx	DD-MMM-YYYY	xxxx	xxxx	Normal/Abnormal	xxxx

Document Title:	Document ID:	BP04-01
Statistical Analysis Plan	Version Number:	3.1
	Effective Date:	25-Nov-2021

[Listing 16.3.7. Listing of Patient Urinalysis Pregnancy test](#)

Patient No	Visit	Urine Pregnancy Test performed	Date and Time of Assessment	Result
xx-xxx	Xxxx	Yes/No	DD-MMM-YYYY/HH:MM	Positive/Negative
xx-xxx	xxxx	Yes/No	DD-MMM-YYYY/HH:MM	Positive/Negative
xx-xxx	xxxx	Yes/No	DD-MMM-YYYY/HH:MM	Positive/Negative
xx-xxx	xxxx	Yes/No	DD-MMM-YYYY/HH:MM	Positive/Negative
xx-xxx	xxxx	Yes/No	DD-MMM-YYYY/HH:MM	Positive/Negative

Document Title:		Document ID:	BP04-01
Statistical Analysis Plan		Version Number:	3.1
		Effective Date:	25-Nov-2021

Listing 16.3.8. Listing of Patient Pregnancy Form

Patient No	Date Pregnancy was confirmed	Date of Last Menstrual Period	Date of Estimated delivery	Outcome of Pregnancy	Live Birth Date	Pregnancy Status	Elective abortion Date	Spontaneous/misses Date	Ectopic abortion Date
xx-xxx	DD-MMM-YYYY	DD-MMM-YYYY	DD-MMM-YYYY	Xxxx	DD-MMM-YYYY	Xxxx	DD-MMM-YYYY	DD-MMM-YYYY	DD-MMM-YYYY
xx-xxx	DD-MMM-YYYY	DD-MMM-YYYY	DD-MMM-YYYY	Xxxx	DD-MMM-YYYY	Xxxx	DD-MMM-YYYY	DD-MMM-YYYY	DD-MMM-YYYY
xx-xxx	DD-MMM-YYYY	DD-MMM-YYYY	DD-MMM-YYYY	Xxxx	DD-MMM-YYYY	Xxxx	DD-MMM-YYYY	DD-MMM-YYYY	DD-MMM-YYYY
xx-xxx	DD-MMM-YYYY	DD-MMM-YYYY	DD-MMM-YYYY	Xxxx	DD-MMM-YYYY	Xxxx	DD-MMM-YYYY	DD-MMM-YYYY	DD-MMM-YYYY
xx-xxx	DD-MMM-YYYY	DD-MMM-YYYY	DD-MMM-YYYY	Xxxx	DD-MMM-YYYY	Xxxx	DD-MMM-YYYY	DD-MMM-YYYY	DD-MMM-YYYY

Document Title:	Document ID:	BP04-01
Statistical Analysis Plan	Version Number:	3.1
	Effective Date:	25-Nov-2021

Listing 16.3.9.1. Listing of Patient Concomitant Medication

Patient No	Visit	Patient have any other concomitant medication during visit	Any changes in concomitant or taking new medication since last visit
xx-xxx	xxxx	Yes/No	Yes/No
xx-xxx	xxxx	Yes/No	Yes/No
xx-xxx	xxxx	Yes/No	Yes/No
xx-xxx	xxxx	Yes/No	Yes/No
xx-xxx	xxxx	Yes/No	Yes/No

[figure not shown]
Document Title:		Document ID:	BP04-01
Statistical Analysis Plan		Version Number:	3.1
		Effective Date:	25-Nov-2021

Listing 16.3.9.2. Listing of Patient Prior and Concomitant Medication

Patient No	Patient receive any Prior or concomitant medications	Seq . No.	Medication Name	Start Date/ Stop Date	Ongoing	Indication	Indication Description	Dosage Form	Dose	Unit	Route	Frequency
XX-XXX	Yes/No	Xx	XXXX	DD-MMM-YYYY/ DD-MMM-YYYY	XXXX	XXXX	XXXX	XXXX	XXXX	XXXX	XXXX	XXXX
XX-XXX	Yes/No	Xx	XXXX	DD-MMM-YYYY/ DD-MMM-YYYY	XXXX	XXXX	XXXX	XXXX	XXXX	XXXX	XXXX	XXXX
XX-XXX	Yes/No	Xx	XXXX	DD-MMM-YYYY/ DD-MMM-YYYY	XXXX	XXXX	XXXX	XXXX	XXXX	XXXX	XXXX	XXXX
XX-XXX	Yes/No	Xx	XXXX	DD-MMM-YYYY/ DD-MMM-YYYY	XXXX	XXXX	XXXX	XXXX	XXXX	XXXX	XXXX	XXXX
XX-XXX	Yes/No	xx	XXXX	DD-MMM-YYYY	XXXX	XXXX	XXXX	XXXX	XXXX	XXXX	XXXX	XXXX

Document Title:	Document ID:	BP04-01
Statistical Analysis Plan	Version Number:	3.1
	Effective Date:	25-Nov-2021

[figure not shown]
Figure 14.2.1. Figure of Time to first Asthma Exacerbation

Programmer Note: Kaplan-Meier Curve format will change.; X-axis= Time (Days) and y- axis=Probability

Document Title:	Document ID:	BP04-01
Statistical Analysis Plan	Version Number:	3.1
	Effective Date:	25-Nov-2021

[figure not shown]
Figure 14.2.2. Figure of Number of Exacerbation

Programmer Note: X-axis= Time point and y- axis= No. of Exacerbations

Document Title:	Document ID:	BP04-01
Statistical Analysis Plan	Version Number:	3.1
	Effective Date:	25-Nov-2021

Figure 14.2.3. Figure of Mean of Exacerbation

Programmer Note: X-axis= Time point and y- axis= Mean of Exacerbations

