6.3.2 Secondary Endpoint Analysis

All Secodary Endpoints will be summarized based on the Evaluable Analysis Set.

Descriptive summaries will be provided for the Asthma Exacerbation. All the continuous variables will be summarized by n, mean, standard deviation, minimum, median and maximum values. All the categorical variables will be summarized as frequency, percentage of Patients in each category and corresponding 95% CI (using Clopper-Pearson exact Method, where appropriate).

Time from first dose of study treatment to the first asthma exacerbation will be calculated as follows: Start Date of first asthma exacerbation minus Date of first dose of study treatment plus 1. The time to first asthma exacerbation for participants who do not experience an asthma exacerbation during the study period will be censored at 24 weeks, or at the time point after which an exacerbation could not be assessed (for lost-to-follow-up participants). The data will be summarised through median time to the first asthma exacerbation along with the 95% CI of median (as per availability of data) and displayed graphically using a KM plot.

Blood Eosinophils level will be summarized based on the Evaluable Analysis Set.

Blood Eosinophils will be summarised descriptively for actual values and change from baseline at week 4, 16, 24 using the number of observations, arithmetic mean, SD, median, 25th and 75th percentiles, and minimum and maximum values.

The Blood Eosinophils in this study is to evaluate the change from baseline to Post-baseline will be analysed using Paired t – test / Wilcoxon signed-rank test at 5% level of significance.

Change from baseline will be determined as:

Change from Baseline = (Post-baseline – Baseline)

Percent Change Change from Baseline = ([Post-baseline – Baseline] / Baseline) X 100

Overall Investigators Assessment will be summarized based on the Evaluable Analysis Set.

Descriptive summaries will be provided for the Overall Investigators Assessment.

Document Title:	Document ID:	BP04-01
Statistical Analysis Plan	Version Number:	3.1
	Effective Date:	25-Nov-2021

All the categorical variables will be summarized as frequency, percentage of Patients in each category and corresponding 95% CI (using Clopper-Pearson exact Method, where appropriate).

7. References

1. ICH E3 Guideline_International Council for Harmonisation

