Table 14.1.6. Patient Administration of Benralizumab (Evaluable Analysis Set)

	N = xx
	n (%)
Visit x	
Patient administer study Medication at this visit (N*=xxx)	
Yes	xx (xx.xx)
No	xx (xx.xx)

- The Capital "N" in the column header represents the total number of Evaluable Analysis Set.
- The small "n" in summary statistics represents the total number of patients in the row category.
- All percentages are based on N* i.e. the total number of patients of Evaluable Analysis set at the visit.
-
- Programmer Note: Visit x- Visit 1, Visit 2 and visit 3
- Source: Listing 16.1.6.1

Document Title:	Document ID:	BP04-01
Statistical Analysis Plan	Version Number:	3.1
	Effective Date:	25-Nov-2021

Table 14.1.7. Summary of Overdose (Evaluable Analysis Set)

	N = xx
	n (%)
Overdose of study intervention recorded	
Yes	xx (xx.xx)
No	xx (xx.xx)
Missing	xx (xx.xx)
Adverse Event occurred due to overdose	
Yes	xx (xx.xx)
No	xx (xx.xx)
Missing	xx (xx.xx)
Overdose Accidental	
Yes	xx (xx.xx)
No	xx (xx.xx)
Missing	xx (xx.xx)

- The Capital "N" in the column header represents the total number of Evaluable Analysis Set.
- The small "n" in summary statistics represents the total number of patients in the row category.
- All percentages are based on the Evaluable Analysis set.
- Source: Listing 16.1.6.2

Document Title:	Document ID:	BP04-01
Statistical Analysis Plan	Version Number:	3.1
	Effective Date:	25-Nov-2021

Missing	Xx
Mean (SD)	xx.x (xx.xx)
Median	xx.x
(min, max)	(xx.xx, xx.xx)
(25 th percentiles, 75 th percentiles)	(xx.xx, xx.xx)

- The Capital "N" in the column header represents the total number Evaluable Analysis Set.
- The small "n" in summary statistics represents the total number of patients.
- Percentages are based on number of Evaluable Analysis Set.
- SD = Standard Deviation, min=minimum, max=maximum
- Source: Listing 16.1.7

Document Title:	Document ID:	BP04-01
Statistical Analysis Plan	Version Number:	3.1
	Effective Date:	25-Nov-2021

Table 14.2.1.1. Summary of Asthma and Exacerbation (Evaluable Analysis Set)

	N = xx	
	n (%)	95% CI
Visit 1		
Significant History of Asthma with Eosinophilic Phenotype		
Yes	xx (xx.xx)	(xx.xx, xx.xx)
No	xx (xx.xx)	(xx.xx, xx.xx)
Missing	xx (xx.xx)	(xx.xx, xx.xx)
Disease Duration (months)		
n	Xx	
Missing	Xx	
Mean (SD)	xx.x (xx.xx)	
Median	xx.x	
(min, max)	(xx.xx, xx.xx)	
(25 th percentiles, 75 th percentiles)	(xx.xx, xx.xx)	
Patient Experience Exacerbation in the previous 12 months		
Yes	xx (xx.xx)	(xx.xx, xx.xx)

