No	xx (xx.xx)	(xx.xx, xx.xx)
Missing	xx (xx.xx)	(xx.xx, xx.xx)
Visit x		
Patient Experience any new Exacerbation or change in existing Exacerbation since last visit		
Yes	xx (xx.xx)	(xx.xx, xx.xx)
No	xx (xx.xx)	(xx.xx, xx.xx)
Missing	xx (xx.xx)	(xx.xx, xx.xx)

- The Capital "N" in the column header represents the total number of Evaluable Analysis Set.
- The small "n" in summary statistics represents the total number of patients.
- All Percentages rows are based on the total number of Evaluable Analysis Set.
- 95% CI calculate will be using Clopper-Pearson Exact method.
- Programmer Note: Visit x- Visit 2, Visit 3, Visit 4 and Visit 5
- Source: Listing 16.2.1.1 and Listing 16.2.1.2

Document Title:	Document ID:	BP04-01
Statistical Analysis Plan	Version Number:	3.1
	Effective Date:	25-Nov-2021

Table 14.2.1.3. Summary of Before and After Treatment Exacerbation (Evaluable Analysis Set)

N = xx

**Exacerbation
before study**

N	xx
Missing	xx
Mean (SD)	x.x (x.xx)
Median	x.x
(min, max)	(x,x)
(25th Percentile, 75th Percentile)	(x.xx, x.xx)

**Exacerbation at
end of study**

n	xx
Missing	xx
Mean (SD)	x.x (x.xx)
Median	x.x
(min, max)	(x,x)
(25th Percentile, 75th Percentile)	(x.xx, x.xx)
P-value	x.XXXX

**Annualized
exacerbation
rate**

x.xx

- The column header's capital "N" denotes the total number of Evaluable Analysis Sets.
- The modest "n" in the number of patients suffering from exacerbation.
- The annual rate for each patient was calculated by dividing the total number of exacerbations by the number of days participated in the study and multiplying by 365.
- Source: Listing 16.2.2.1, Listing 16.2.2.2 and Listing 16.2.2.3

Document Title:	Document ID:	BP04-01
Statistical Analysis Plan	Version Number:	3.1
	Effective Date:	25-Nov-2021

Table 14.2.2. Summary of Time to first Exacerbation (Evaluable Analysis Set)

		N=xxx
Patient Asthma Exacerbation, n (%)		
Yes		xx(xx.xx)
No		xx(xx.xx)
Duration of Patient First Asthma Exacerbation (Days)		
n		Xx
missing		xx
Mean (SD)		xx.x (xx.xx)
Median		xx.x
(min , max)		(xx.xx, xx.xx)
(25 th Percentile, 75 th Percentile)		(xx.xx, xx.xx)
Estimate for Time to Response (Days)		
Median		xx.x
95 % CI		(xx.xx, xx.xx)

- The Capital "N" in the column header represents the total number of Evaluable Analysis Set.
- The small "n" in summary statistics represents the total number of patients
- Estimate for Time to Response using Kaplan-Meier method.

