Patient No	Any Overdose of study interventional recorded	Any Adverse Event Occurred due to Overdose	Seq. of AE	Date of Overdose	Visit of Overdose	Overdose Accidental	Possible Cause
XX-XXX	Yes/No	Yes/No	Xx	DD-MMM-YYYY	Xx	Yes/No	Xxxx
XX-XXX	Yes/No	Yes/No	Xx	DD-MMM-YYYY	Xx	Yes/No	Xxxx
XX-XXX	Yes/No	Yes/No	Xx	DD-MMM-YYYY	Xx	Yes/No	Xxxx
XX-XXX	Yes/No	Yes/No	Xx	DD-MMM-YYYY	Xx	Yes/No	Xxxx
XX-XXX	Yes/No	Yes/No	xx	DD-MMM-YYYY	xx	Yes/No	Xxxx

Document Title:	Document ID:	BP04-01
Statistical Analysis Plan	Version Number:	3.1
	Effective Date:	25-Nov-2021

Listing 16.1.7. Listing of Patient Pulmonary Function Test

Patient No	Pulmonary function test using Spirometer performed	Date and Time of Assessment	Pre-Bronchodilator of Assessment	Unit	Result	Patient have any historical proof of Post- Bronchodilator reversibility within 12 months		Date of Assessment	Post-Bronchodilator of Assessment		
						Yes/No	Yes/No		Unit	Result	
xx-xxx	Yes/No	DD-MMM-YYYY/HH:MM	xxxx	Xxxx	Xxxx	Yes/No	Yes/No	Xxxx	Xxxx	Xxxx	
xx-xxx	Yes/No	DD-MMM-YYYY/HH:MM	xxxx	Xxxx	Xxxx	Yes/No	Yes/No	Xxxx	Xxxx	Xxxx	
xx-xxx	Yes/No	DD-MMM-YYYY/HH:MM	xxxx	Xxxx	Xxxx	Yes/No	Yes/No	Xxxx	Xxxx	Xxxx	
xx-xxx	Yes/No	DD-MMM-YYYY/HH:MM	xxxx	Xxxx	Xxxx	Yes/No	Yes/No	Xxxx	Xxxx	Xxxx	
xx-xxx	Yes/No	DD-MMM-YYYY/HH:MM	xxxx	Xxxx	Xxxx	Yes/No	Yes/No	Xxxx	Xxxx	Xxxx	

Document Title:	Document ID:	BP04-01
Statistical Analysis Plan	Version Number:	3.1
	Effective Date:	25-Nov-2021

Listing 16.2.1.1. Listing of Patient Asthma and Exacerbation History

Patient No	Significant history of Asthma with Eosinophilic	Date of Diagnosis	Disease Duration (Years: Months)	Patient Experience exacerbation in the previous 12 months
xx-xxx	Yes/No	DD-MMM-YYYY	YY:MM	Yes/No
xx-xxx	Yes/No	DD-MMM-YYYY	YY:MM	Yes/No
xx-xxx	Yes/No	DD-MMM-YYYY	YY:MM	Yes/No
xx-xxx	Yes/No	DD-MMM-YYYY	YY:MM	Yes/No
xx-xxx	Yes/No	DD-MMM-YYYY	YY:MM	Yes/No

Document Title:	Document ID:	BP04-01
Statistical Analysis Plan	Version Number:	3.1
	Effective Date:	25-Nov-2021

[Listing 16.2.1.2. Listing of Patient Assessment of Asthma and Exacerbation](#)

Patient No	Visit	Patient Experience any new exacerbation or change in exacerbation since last visit
XX-XXX	xxxx	Yes/No

Document Title:	Document ID:	BP04-01
Statistical Analysis Plan	Version Number:	3.1
	Effective Date:	25-Nov-2021

Listing 16.2.2.1. Listing of Patient Exacerbation (Part 1)

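### SAP Table 14.2.1.3 prints a P-value on raw before and after exacerbation counts with no test or before window stated; on the only pre-study window visible, it would be significant with no drug effect

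*SAP*

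**What the plan says.** In SAP section 8, the shell "Table 14.2.1.3. Summary of Before and After Treatment Exacerbation (Evaluable Analysis Set" has a block for exacerbations before the study, a block for exacerbations at end of study, one P-value and one annualised rate. Minimum and maximum are laid out as integers in both blocks, so they hold counts.

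The footnotes give three things:
- Annualisation, for the on-study period only: "The annual rate for each patient was calculated by dividing the total number of exacerbations by the number of days participated in the study", multiplied by 365.
- The meaning of n: "The modest 'n' in the number of patients suffering from exacerbation".
- The data source: "Source: Listing 16.2.2.1, Listing 16.2.2.2 and Listing 16.2.2.3".

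No footnote names a test or a before window. For exacerbations, SAP 6.3.2 says "Descriptive summaries will be provided for the Asthma Exacerbation" and adds a Kaplan-Meier analysis. Its paired t test or "Wilcoxon signed-rank test at 5% level of significance" is stated for blood eosinophils. Elsewhere, Table 14.2.1.1 carries the item "Patient Experience Exacerbation in the previous 12 months", and Listing 16.2.1.1 records that history only as Yes/No.

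Protocol 9.4.3 plans an exact Poisson 95% confidence interval for the annualised rate and no before/after comparison. Protocol 8.3.1 sets follow-up at about 24 weeks. Inclusion Criterion 4 requires at least 2 exacerbations in the preceding 12 months, leaving out the last 30 days before consent.

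**The concern.** A programmer working from this shell would have to choose the test, the before window and the handling of patients without events. The most obvious before figure is the 12-month history. Counts over 12 months and over 24 weeks differ even if nothing changes in the patients, and a paired test would report that difference as highly significant.

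A per-year scale cures the unequal windows but leaves a second problem. Patients enter because they had at least 2 recent exacerbations, so their later rate tends to be lower without treatment. Protocol 6.4 acknowledges that there is no control group to measure that fall.

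At stake is a P-value beside a before/after contrast that readers would take as evidence of effectiveness.

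**Working it through.** **The plan's own figures.** The documents give no figure for this P-value. The N used below is in the SAP Table 14.1.1.1 footnote and reproduces: 154 enrolled − 10 screen failures − 6 not dosed = 138.

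**Step 1. Window length alone.** Before = 365 days (12 months); after = 24 × 7 = 168 days. At an unchanged rate the expected ratio is 168/365 = 0.46, a 54% fall.

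**Step 2. What a paired test makes of it.** Assume Poisson counts, the same rate r per year in both periods, and no entry selection. The expected means are b = r and a = r × 168/365, and z ≈ (b − a)/√((a + b)/138). The documents give no value for r, so a range is shown.

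| r per year | b | a | z | trials with p<0.05 |
|---|---|---|---|---|
| 0.5 | 0.50 | 0.23 | 3.7 | about 97% |
| 1 | 1.00 | 0.46 | 5.2 | about 100% |
| 2 | 2.00 | 0.92 | 7.4 | 100% |
| 3 | 3.00 | 1.38 | 9.1 | 100% |

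The last column is from simulation with the paired t test. At 0.5 per year, repeated runs gave 96% to 97%. With equal windows of 168 days the same test gives 4.6% to 5.1%, so the excess comes from the windows.

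**Step 3. Adding the entry rules.** Model with no drug effect: at least 2 events in 365 − 30 = 335 days; then 30 + 14 = 44 event-free days (Exclusion Criteria 7 and 8, with the full 14-day screening); then 168 days on study. Assumed source rates are 1 to 6 per year, with Poisson counts or gamma-Poisson counts of shape 2 or 1, giving 18 settings. Raw counts fall by 51% to 81%, and the paired t test gives p<0.05 in 100% of trials in all 18.

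**Step 4. Same model, both periods per year.**

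| Before denominator | Source rate | Change | Paired t, p<0.05 | Wilcoxon, p<0.05 |
|---|---|---|---|---|
| 365 days | 1–3 | 9% to 58% fall | 24% to 100% | 50% to 100% |
| 365 days | 4–6 | 5% fall to 6% rise | 5% to 17% | 6% to 31% |
| 335 days | 1–3 | 16% to 61% fall | 69% to 100% | 98% to 100% |
| 335 days | 4–6 | 2% to 13% fall | 6% to 51% | 27% to 95% |

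Only the paired t test with a 365-day denominator comes near its nominal 5% at 4 to 6 per year. Its 17% there belongs to a setting with an apparent rise, so it is not a false benefit. Even without entry selection, the Wilcoxon test on per-year rates from 335 and 168 days gives 24% to 28%.

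**Step 5. The rate row.** If all 138 patients complete, person-time is 138 × 168/365 = 63.5 years. As an illustration, 40 events would give 40/63.5 = 0.63 per year, with an exact Poisson 95% interval of 0.45 to 0.86. The shell shows the rate only. In the 12 gamma-Poisson settings the exact interval covers the true rate in 82% to 94% of trials; a robust Poisson interval covers it in 94% to 96%.

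**Step 6. The note on n.** If event-free patients were dropped from the on-study mean, the raw fall in the Step 3 model would be 42% to 48% instead of 51% to 81%. The wording therefore changes the displayed result.

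**Step 7. Time origin.** Protocol 8.3.1 counts follow-up from enrolment, which Protocol section 5 defines as consent. Screening can add 14 days, and Exclusion Criterion 8 makes these event-free. Counting them would lower the rate by up to 14/(168 + 14) = 7.7%.

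**The case against.** - **The 12-month window is an inference.** This is correct, and the result in Step 2 is conditional on it. A reader might infer that the plan definitely compares 12 months with 24 weeks. The documents do not say so: the table does not cite the history listing, and the Table 14.2.1.2 shell, which might define the window, is not in the supplied text.
- **The data may exist.** A reader might infer that no pre-study counts are collected, because the history item is Yes/No. The documents do not support that. The table's source line implies that Listings 16.2.2.1 to 16.2.2.3 hold the before events; Listing 16.2.2.1 has onset dates, and the Schedule of Activities marks exacerbation assessment at screening and Day 1. The window is still unstated.
- **The no-hypothesis statement.** SAP 6.2 and Protocol 9.1 say that none is tested. This is weak ground against one row, because the SAP plans 5% tests for vital signs, laboratory values and eosinophils. The case rests on the windows and the entry rule.
- **The alternative reading of n.** If only patients with an on-study event are compared, window length alone no longer guarantees significance: at 1 per year, roughly 5% to 60% of trials reach p<0.05, depending on heterogeneity and test. Adding the entry rule brings this back to 100% at the rates checked (1 to 3 per year).
- **The per-year results rest on assumptions.** This stands. For example, leaving out the 44 event-free days gives 56% to 78% at 3 per year (335 days, paired t), against 69% or more in Step 4.
- **The SAP supersedes the protocol.** SAP section 1 says so for the differences it describes. It describes no decision to drop the confidence interval, so the omission reads as an oversight, unless the missing shell supplies it.

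**Conclusion.** The defect is real: a P-value is printed on raw before and after counts, with no test or before window in the visible text. If the 12-month history supplies the before count, the P-value is significant in essentially every trial without any drug effect, given 138 patients, Poisson-type counts and a rate of 1 per year or more.

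On a per-year scale the false signal ranges from large to close to nominal, depending on the rate, the denominator and the test. A reader might infer that it is equally severe on that scale; the figures do not support that. After selection on prior exacerbations the two rates may truly differ, so the error lies in attributing the difference to the drug in a study without a control group.

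The missing interval and the ambiguous n are separate, smaller faults in the same table. All of this concerns a secondary display and should be fixed, but it does not touch the primary safety objective.

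**What to change.** 1. Delete the P-value row from Table 14.2.1.3.
2. Report the on-study annualised rate as exacerbations per person-year over all Evaluable patients, counting those without an event as 0, with the exact Poisson 95% interval of Protocol 9.4.3. Reword the note on n to match. A robust Poisson interval is an optional addition, because the exact one is too narrow if patients' rates differ.
3. State when person-time starts and reconcile it with Protocol 8.3.1, which counts from enrolment.
4. Correct Protocol 9.4.3, which describes an annualised rate as being per 24 weeks and as a percentage, to events per person-year.
5. Show any pre-study figure descriptively only, per person-time, with its window and source listing, and a note that entry required at least 2 prior exacerbations, so some fall may occur without any treatment effect. If no pre-study count is held, drop the row.

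The cost is one table shell, its footnotes and a wording correction in the protocol. The on-study rate and interval need no new data. The downside is a less favourable-looking before/after display and a little more analysis work.
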